The long term goal of the research is to develop non-invasive brain stimulation as an evidence-based tool to facilitate abstinence during the first week after a quit attempt, as this is a robust predictor of 6-month treatment outcomes with traditional pharmacotherapeutic and behavioral interventions. The next step in pursuit of that goal is to systematically and parametrically evaluate the efficacy of two promising TMS treatment strategies (LTP-like stimulation to the mPFC (Aim 1), LTP-like stimulation to the dIPFC (Aim 2)) as tools to change smoking behavior and brain reactivity to smoking cues. These aims will be addressed in serial (Aim 1 Years 1-3, Aim 2 Years 3-5). A randomized, double-blind, sham-controlled design will be used for each aim. In total, 138 smokers will be recruited from the tri-county area surrounding Winston-Salem, NC. Current cigarette smokers seeking to quit smoking and willing to set a quit date will be recruited from the tri-county area using digital and print advertising in diverse media outlets. Following informed consent and screening, participants will be randomized to receive real or sham TMS to the mPFC (Aim 1, Years 1-3) or the dlPFC (Aim 2, Years 3-5) (see Table 1 and TMS Procedures below for more details regarding sham controls and double blinding procedure). During the Treatment Phase, participants will receive 10 sequential days of TMS (with additional behavioral and MRI scanning (see Table 1). Participants will receive TMS at least 3 times a week for a total of 10 TMS sessions. During the follow-up phase, participants will receive 4 maintenance TMS sessions once a week for 4 weeks. During the Follow Up Phase, behavioral assessments will be acquired weekly for the first 4 weeks (see Table 2), and daily EMA will be acquired. Consistent with the CNDS model, the primary hypotheses are that LTP-like stimulation to the mPFC and LTP-like stimulation to the dlPFC will both lead to a decrease in

smoking cue-reactivity in the salience network (neuroimaging outcome), and cigarette value (behavioral outcome) but that directly targeting the value circuit (mPFC) will be more efficacious. Additionally, we will test the hypothesis that individuals with higher discounting rates and cigarette valuation at baseline will respond more to the stimulation strategies compared to those with lower baseline discounting and valuation (Exploratory Aim).

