Study Visit Procedures: At all visits, individuals will provide a urine screen to detect recent use of drugs of abuse and pregnancy, a breath carbon monoxide (CO) sample to detect recent cigarette smoking, and a breath sample to test for recent alcohol use. During the consent visit, visits 1, 6, 10 and follow up visits samples will be collected to determine cotinine (nicotine metabolites) levels in the urine. Samples will be taken from the urine sample provided for the drugs of abuse screen, no additional samples will be required from the participant. At visits 1, 6, 10 and follow up visits (Assessment visits), participants will complete a battery of behavioral assessments following active TMS or sham (see Table 2). MRI scanning (at visits 1 and 10) will occur prior to TMS in order to isolate cumulative, rather than acute, effects of TMS. At all visits participants will be required to provide a CO reading at least 50% of their baseline CO measure to ensure they are at least 6 hours deprived from cigarettes. Cigarette deprivation will be use to increase craving and responding for cigarettes. Short term cigarette deprivation has known amplification effects on the brain response to smoking cues (93, 94). Moreover, we have extensive experience with successfully using this deprivation procedure (33, 41).

Table 2 1. Biochemical and self-report assessment of tobacco use and dependence						
Measure	Time (Min.)	Visits	Description			
Carbon monoxide (CO Level)	1	1-10, and follow-ups	Breath CO provides an accurate measure of recent exposure to CO , including from smoking combustible tobacco products (95). The CO measurement will be used to determine recency of smoking.			
Timeline Follow-Back (TLFB) interview	5	1, 6, 10, and follow-ups	This self-reported tobacco product use interview asks participants to retrospectively estimate the number of tobacco products they've used each day for the past 30 days or since the previous assessment, whichever is fewer (89).			
Fagerström (FTND)	3	1, 6, 10, and follow-ups	This 6-item questionnaire quickly assesses degree of cigarette dependence (96, 97). Test for Cigarette Dependence.			
2. Measures of t	tobacco pr	oduct value an	d sensitivity (**PRIMARY DEPENDENT MEASURES)			

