After the MRI scanning visits participants will be escorted into the Brain Stimulation Research Laboratory ([name] research suite) where scalp localization will be performed for the TMS procedure. The Cartesian position of the coil (X,Y,Z) will be determined by standardized positions from the EEG 10-20 system: 1) AFZ will be used for the mPFC stimulation (Aim 1), 2) F3 will be used for the left dlPFC stimulation (Aim 2). The angular position of the coil (pitch, yaw, roll) will be determined by the individual's cortical geography using the individual's T1 scan for guidance. The locations and coil orientation will be indicated on a nylon cap which will be worn during the TMS sessions. We will then determine the participant's resting motor threshold (RMT, the minimal amount of stimulation required over the hand area of the primary motor cortex to induce contraction of the APB muscle of the hand 50% of the time) via the standardized PEST procedure (106, 107). The procedures for acquiring the motor threshold, performing cortical localization, standardized procedures, blinding, establishing standardized paradigms and training regimens for all staff, as well as safety and ring the experimental procedures are consistent with our prior publications (7,27, 54, 63, 69, 78, 111). We will also publish a Standard Operating Procedure document and video file as supplementary material with any publications that arise from this project (as in 111, supplement).

For Aim1 (Strategy 1) stimulation will be over mPFC. For Aim 2 (Strategy 2) stimulation will be over the left dlPFC. The Aims will be pursued in serial, with a 2:1 active versus sham randomization for each Aim. Participants will receive 20 trains of stimulation (1200 pulses total; each train: 3 pulse bursts presented at 5Hz, 15 pulses/sec for 2 sec, 8 sec rest, 10 pulses/train; 110% RMT, MagPro) using a figure 8 coil (Coil Cool-B65 A/P). This is the iTBS sequence initially published (3) which has been used in clinical depression treatment (46). During each real and sham TBS session each day the amplifier output will be escalated ("ramping" in 5% increments over 30 seconds) up to 80% to 110% RMT to enhance tolerability. The time between the end of the TBS procedures and the beginning of the behavioral assessments will be compiled and used as covariates in subsequent analyses.

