Hypothesis Aim 1: Based on the framework predicted by CNDS theory, and preliminary work (see Study 4), we anticipate that mPFC stimulation will lead to a decrease in brain reactivity to cues during the "allow" condition (passive limbic engagement). We will analyze the neuroimaging data in concert with the behavioral data, evaluating the hypotheses that 1) mPFC iTBS will decrease the brain reactivity to cues in the 'allow' condition (with no consistent link to the 'resist' condition) and that 2) this will be related to the behavioral change in a dose-dependent manner. This will be achieved by extracting the average BOLD signal timecourse and the percent signal change during the CIG versus NEU blocks from a priori anatomically defined regions of interest (ROIs), including the striatum (ventral striatum and dorsal striatum), insula, inferior frontal gyrus, and anterior cingulate cortex. Ventral striatal and dorsal striatal ROIs are derived from the FSL Oxford-GSK-Imanova striatal atlas, mapped via probabilistic diffusion tractography (109) in agreement with anatomical projection zones from the frontal cortex (1). Hypothesis Aim 2: Based on the framework predicted by CNDS theory, and prior studies of dlPFC stimulation in smokers (4-9), we anticipate that dIPFC stimulation will lead to an increase in executive control circuitry (left dlPFC, posterior parietal cortex) during the "resist" condition (executive engagement). As in Aim 1, we will analyze the neuroimaging data in concert with the behavioral data, evaluating the hypotheses that 1) dIPFC iTBS will decrease the brain reactivity to cues in the "resist" condition (with no consistent link to the "allow" condition) and that 2) this will be related to the behavioral change in a dose-dependent manner. The ROI based outcomes of Aim 2 will be compared with the outcomes of Aim 1 using standard general linear modeling as well as a data-driven hierarchical model (see Integration below). As an experimental control, for both Aims we will also calculate the percent signal change from the primary motor cortex, a region which should not be differentially modulated by mPFC or dIPFC stimulation. Although some studies have used the visual cortex as a control region a recent meta-analysis by our group demonstrated that the visual cortex is typically activated more to drug cues than neutral cues (78). Secondary functional connectivity analysis: Additionally, an exploratory seed-based functional connectivity analysis using psychophysiological interactions (PPIs) will be performed using the TMS stimulated ROIs (mPFC and dlPFC) and the striatal target regions (ventral striatum, dorsal striatum- defined above) as seed regions. These data will be compiled across participants and compared between the mPFC and dIPFC stimulation days. Group analyses will be performed using a random effects model limiting significant clusters to those that meet p<0.05 family-wise error corrected.

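### The exploratory connectivity analysis compares mPFC with dlPFC stimulation days, but each participant is assigned only one site and the sentence names no sham or visit term

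*Combined protocol and SAP*

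**What the plan says.** Under Outcome Measure(s), the neuroimaging text ends with a secondary connectivity paragraph: "an exploratory seed-based functional connectivity analysis using psychophysiological interactions (PPIs) will be performed using the TMS stimulated ROIs", with the mPFC, the dlPFC and the ventral and dorsal striatum as seeds. The contrast follows: "These data will be compiled across participants and compared between the mPFC and" dlPFC stimulation days. The group model is then given: "Group analyses will be performed using a random effects model limiting significant clusters to those that meet p<0.05 family-wise error corrected". No treatment arm and no visit is named.

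The design is described elsewhere:

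- **Site.** The Design section assigns participants to "real or sham TMS to the mPFC (Aim 1, Years 1-3) or the dlPFC (Aim 2, Years 3-5"), one site each.
- **Randomisation.** The TMS Treatment section says: "The Aims will be pursued in serial, with a 2:1 active versus sham randomization for each Aim".
- **Scans.** Study Visit Procedures says: "MRI scanning (at visits 1 and 10) will occur prior to TMS". The stated reason is to capture cumulative rather than acute effects.
- **Numbers.** The Analytical Plan gives 138 participants, 69 per Aim, split 46 active and 23 sham.

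**The concern.** Comparing stimulation days at two sites is the language of a crossover, in which one person has a day at each site. This trial has no such person. If the sentence is instead read as Aim 1 against Aim 2, the comparison is between different people recruited in different years. The only randomised factor, active versus sham, does not appear in it, and neither does the pre-treatment scan.

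The trial's premise is that stimulation selectively modulates two frontal-striatal loops. The PPI is the only stated analysis that could show a treatment effect on connectivity in those loops, because the Exploratory Aim uses baseline connectivity only, as a predictor. Followed literally, the sentence gives no sham-controlled estimate of a change in connectivity. Left open, the contrast would have to be chosen after the data are in hand.

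**Working it through.** **1. The plan's allocation, and the number of site pairs.** 2 Aims × (46 active + 23 sham) = 2 × 69 = 138, which reproduces the stated total; 46/23 gives the stated 2:1. The total is reached only by adding two separate sets of 69. Planned participants with both an mPFC and a dlPFC day: 0 of 138. The Sample Size section speaks of randomisation to four groups, but four groups would still give each person one site.

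**2. What the scans contain.** The Visit 1 scan precedes all stimulation, so a site contrast on Visit 1 data contains no TMS effect. The Visit 10 scan follows the earlier sessions but also carries any difference between the cohorts that was there before treatment. Only the change from Visit 1 to Visit 10, set against sham, isolates a cumulative treatment effect.

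**3. What a plain between-Aim contrast would pick up.** The plan's retention of 78% gives 138 × 0.78 = 107.6, its stated 108. That is 54 per Aim, or 36 active and 18 sham. Suppose TMS has no effect and the two cohorts differ by *s* standard deviations on a connectivity estimate. The documents give no value for *s*, so it is an assumption shown over a range. With SE = √(2/n) and a two-sided test at 0.05, the chance of a significant site difference is 1 − Φ(1.96 − s/SE) + Φ(−1.96 − s/SE):

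| Assumed shift *s* (SD) | 36 vs 36, active only | 54 vs 54, if arms were pooled |
|---|---|---|
| 0 | 5% | 5% |
| 0.1 | 7% | 8% |
| 0.2 | 14% | 18% |
| 0.3 | 25% | 34% |
| 0.5 | 56% | 74% |

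For example, with s = 0.3 and n = 36: SE = √(2/36) = 0.236, s/SE = 1.27, result 25%. These rates are for one estimate at unadjusted 0.05. They show the direction of the problem and are not the error rate of the cluster-corrected analysis.

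**4. What the corrected site contrast costs in precision.** In SD units of the measure analysed, with equal SDs and 36:18 per Aim:

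- Plain active-versus-active contrast: √(2/36) = 0.236.
- Sham-adjusted effect within one Aim: √(1/36 + 1/18) = 0.289.
- Difference between two such effects: √2 × 0.289 = 0.408.

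The standard error of the corrected site comparison is 0.408/0.236 = 1.73 times as large. Adjustment for Visit 1 may recover some of this; the documents give no correlation from which to say how much.

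**5. The plan's own model for behaviour.** For the behavioural outcomes the plan names time, group (real or sham) and their interaction. The connectivity paragraph has no counterpart, although the sham arms and both scans are already planned.

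**The case against.** The strongest reply is that this is one loosely worded sentence in an analysis labelled secondary and exploratory. Stimulation days may simply mean the scans of the two cohorts, and in a sham-controlled trial with scans timed for cumulative effects, arm and visit terms could be taken as understood. No primary hypothesis or sample size rests on it.

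Much of this stands, and it limits what may be inferred:

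- A reader might infer that the plan pools active with sham and ignores Visit 1. The text does not say so; it is silent on both. The pooled column above is therefore a conditional case.
- A reader might infer that no mPFC versus dlPFC comparison is possible. That goes too far. The difference between the two Aims' sham-adjusted changes is a valid estimate of a relative site effect, though a non-concurrent one. Relative efficacy of the sites is a stated purpose of the trial, so the comparison is worth keeping in that form.
- A reader might infer that the circuit hypothesis is otherwise untested. It is not: the primary ROI analysis examines cue reactivity in the striatum, insula, inferior frontal gyrus and anterior cingulate, with left dlPFC and posterior parietal cortex named for Aim 2.

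What does not stand is that the terms can be left understood. The sentence names a contrast, and the one it names either has no data or does not use the randomisation.

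**Conclusion.** The stated PPI contrast is wrong as written. Its within-person form has 0 planned pairs among 138. Its plain between-Aim form is a non-randomised comparison in which a TMS effect cannot be told from cohort or period. This follows from the assignment of one site per participant, the serial Aims and the scan schedule; only the table of false-positive rates rests on an assumed shift.

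The consequence is confined to an exploratory analysis: primary behavioural and ROI results do not depend on it. It is still worth correcting before analysis, because no other stated analysis could show a treatment effect on frontal-striatal connectivity.

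No power figure is offered for the corrected analysis. A two-group calculation for a single connection at unadjusted 0.05 would not apply to a cluster-corrected analysis with several seeds, and the documents give no connectivity effect size. Imaging numbers may also be lower than 36 and 18 per Aim. The Sample Size section says some participants will have no MRI, and its stated 10% imaging loss is not visible in the 108, which 78% retention alone already produces.

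**What to change.** Replace the sentence on stimulation days with:

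> For each Aim, seed-based PPI estimates will be compared between active and sham for the Visit 1 to Visit 10 change, adjusting for the Visit 1 estimate, with family-wise error correction as stated. Any mPFC versus dlPFC comparison will be the difference between the two Aims' sham-adjusted changes, reported as exploratory and non-concurrent.

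This is a change of wording. It uses the planned scans and arms, needs no added participants, and brings the paragraph into line with the time-by-group form used for behaviour. There is a small cost: the site comparison becomes less precise than a plain between-Aim contrast and must be interpreted cautiously, since the Aims run in different years.

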Behavioral Outcomes: For the treatment phase (10 days of real/sham TBS), the primary behavioral outcomes include Cigarette demand (Q0 and alpha), Craving (QSU Intention, QSU Relief), and Delay Discounting (\$100 and \$1000). For the treatment phase the analysis will be performed using repeated measures ANOVA on change scores from baseline for each visit. The main independent variable in the ANOVA will be time (visits on day 1, 6, 10), group (real or sham) and their interaction. For correlations of observations across visits an AR(1) structure will be considered and compared with other structures such as compound symmetry and a general structure. The primary hypothesis is the interaction. If the interaction effect for an outcome is significant, we will conclude there is statistical evidence of overall treatment effect. If the spaghetti plots suggest trends (e.g., linear, quadratic, or piecewise changes) we will treat time as a continuous variable and fit repeated measures regression models along with group and its interaction with continuous time as independent variables.

Neuroimaging Outcomes: For the treatment phase, primary analysis. Image pre-processing will be conducted with FSL v. 5.0: (FMRIB Analysis Group, Oxford, UK) (108) realignment to the first volume, smoothing with an anisotropic 8-mm Gaussian kernel, high-pass filtering, resampling to 2-mm isotropic voxels, and stereotactic registration to the Montreal Neurological Institute 152-subject average template. Subjects with >3 mm movement (total mean frame displacement across the entire task) will be excluded from analysis.

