
For the follow-up phase: We will test the hypotheses that behavioral change related to Strategy 1 and 2 will be based on an individual's baseline brain cue reactivity data. We will generate Kaplan-Meier curves of behavioral change for the four groups and compare these with cue-reactivity in the MPFC, insula, cingulate (salience network nodes) and striatum using log-rank tests and consider Cox's proportional hazards model to include covariates. Diagnostics will be performed to verify the assumptions such as homoscedasticity and normality. If it is merited, transformations on the outcomes will be considered. Linear contrasts will be utilized to test the hypothesis of equal effects in the two groups at any given time point. Covariates, such as gender and depression that were used to stratify, will be included.

Exploratory Aim: Evaluate baseline frontal striatal connectivity and discounting rate as factors to predict an individual's likelihood of responding to Strategy 1 versus Strategy 2. Finally, will compare the relative efficacy of Strategy 1 versus Strategy 2 on the behavioral change by constructing a computational model. We will test the hypotheses that individuals with a higher ratio of (mPFC-striatal)/(dlPFC-striatal) connectivity will be more likely to have a behavioral change after Strategy 1. Various demographics (e.g. gender, smoking history, socioeconomic status, subclinical depressive symptoms, self-efficacy, & motivation to quit will be evaluated as explanatory variables. This will be achieved by hierarchical linear modeling (HLM v. 7.0, Scientific Software International, Skokie, IL) of the behavioral variables of interest as well as the BOLD signal change in the striatum (caudate) between smoking and image blocks (e.g., CIG vs. NEU) in 'allow' and 'resist' (behavioral change variables nested within treatment (cTBS, iTBS)).

Analytical Plan

Primary data analysis will be done on the Intent to Treat sample (n=138; 69 per Aim: 46 active, 23 sham). Prior to formal statistical analysis, summary statistics for all variables will be obtained and spaghetti plots will be generated. All behavioral outcome measures will be based on standardized composite scores from the literature. We will also use data reduction techniques (such as factor analysis or principle component analysis) to confirm the applicability of the composite scores in our population. Analyses will be performed for each phase separately.

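### As written, the follow-up analysis does not test its hypothesis that response to each strategy depends on baseline cue reactivity: no event is defined and no arm-by-reactivity term is fitted

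*Combined protocol and SAP*

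**What the plan says.** The follow-up paragraph under Outcome Measure(s) gives the hypothesis that "behavioral change related to Strategy 1 and 2 will be based on an individual's baseline brain cue reactivity data". The analysis comes next: "We will generate Kaplan-Meier curves of behavioral change for the four groups and compare these with cue-reactivity in the MPFC, insula, cingulate" and the striatum, "using log-rank tests and consider Cox's proportional hazards model to include covariates". The paragraph then adds "Diagnostics will be performed to verify the assumptions such as homoscedasticity and normality", allows outcomes to be transformed, and says "Linear contrasts will be utilized to test the hypothesis of equal effects in the two groups at any given time point". Gender and depression, the stratifiers, are the only covariates it gives as examples.

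Related text elsewhere:
- Neuroimaging hypotheses (same section): cue reactivity is measured by region as "the percent signal change during the CIG versus NEU blocks".
- Table 2: the cue task has two runs, allow and resist. TLFB is taken at every follow-up visit.
- Design and Table 1: EMA is daily and remote, and its content is not described. Follow-up is labelled a secondary goal (durability).
- Sample Size: the calculation covers the treatment phase only. A later paragraph there says that some participants will have no MRI.

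**The concern.** The hypothesis ties behavioural change to the strategies and makes it depend on a baseline measure. The natural statistical form is effect modification: does the real-versus-sham difference vary with baseline reactivity? The methods named do not contain that comparison. Two things are at stake. First, the survival analysis cannot be run until someone supplies an event, a time origin, a censoring rule and a grouping of reactivity, none of which is prespecified. Second, even with these supplied, the named test answers a different question, so a positive result could be reported as moderation when reactivity merely predicts who relapses, and true moderation could go unseen.

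**Working it through.** **1. What the survival analysis needs, against what the plan gives.**
- Event: the plan says only behavioural change. Abstinence and relapse appear as background and goals, not as a defined endpoint.
- Time origin: none stated. The obvious candidate, the quit date, is itself inconsistent. Table 1 marks treatment day 1 as the quit date, while the text under Interventions and Interactions starts Visit 1 one week before it.
- Censoring rule: none stated.
- Grouping for the log-rank test: reactivity is a continuous percent signal change, and no cut-point is given. The paragraph names four regions and the task has two conditions, so there are at least 4 × 2 = 8 candidate measures.
- Moderation term: none. The contrasts compare two groups at a time point. The Exploratory Aim names a connectivity ratio and discounting rate as predictors. The Analytical Plan adds only regression for independent outcome predictors. Neither contains arm by cue reactivity.

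**2. What each named test would answer if completed.** A log-rank test across the four groups does not use reactivity. A log-rank test of high versus low reactivity tests prognosis. The same test run separately in each arm gives two p-values but no test of the difference between arms. A Cox model with reactivity as a covariate again tests prognosis. Only the product of arm and reactivity tests the hypothesis.

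**3. Illustration.** The plan gives no follow-up event rate, hazard ratio or power, so there is no figure to reproduce. The group sizes follow from Sample Size: 138 × 0.78 = 107.6, matching the stated 108; 108 / 2 = 54 per Aim; at 2:1, 36 active and 18 sham. Everything else is assumed: exponential times with hazard 1/20 per day in sham at mean reactivity, 28-day cut-off, standard normal reactivity, and log hazard ratio −0.5 for active (0 in the null case). There were 800 runs per scenario, so the Monte Carlo standard error is at most √(0.5 × 0.5 / 800) = 1.8 points. Entries are the percentage of runs with p < 0.05.

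| Scenario | Mean events | Log-rank, median split | Cox main term | Cox interaction |
|---|---|---|---|---|
| Null | 41 | 6% | 6% | 5% |
| Prognostic only (+0.5 log HR per SD, both arms) | 34 | 52% | 74% | 5% |
| Moderation averaging out (+0.33 sham, −0.17 active) | 34 | 5% | 4% | 27% |

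In the third scenario the average slope is (18 × 0.33 − 36 × 0.17) / 54, which is about 0, so the tests without the product have nothing to detect.

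**4. Power of the right test.** With D events, arm fractions 1/3 and 2/3, and a median split of reactivity:
- Events for the arm effect: (1.96 + 0.84)² / [(2/9)(ln HR)²]. This gives 74, 136 and 278 for HR 0.5, 0.6 and 0.7.
- Events for an interaction of the same ratio: the same formula with a further factor of 0.25 in the denominator. This gives 295, 542 and 1,111.
- Power: Φ(√(D × 2/9 × 0.25) × |ln ratio| − 1.96).

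| Events per Aim | Ratio of HRs 0.5 | Ratio of HRs 0.25 |
|---|---|---|
| 27 | 13% | 40% |
| 54 (all usable) | 22% | 67% |
| 69 (all randomised) | 27% | 77% |

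The 54 and 69 rows are optimistic: they need an event in every participant, and those without a baseline scan contribute nothing.

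**The case against.** The strongest reply is that this is under-specification, not error. Cox regression is named, it accepts a continuous predictor and an interaction, and its score test extends the log-rank test to a continuous covariate. That stands against a reading that the hypothesis cannot be tested at all. The plan, however, only considers Cox, and only for covariates.

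One could also read the hypothesis as purely prognostic. That would remove the need for the product, but not for the event, time origin, censoring rule and grouping. It also sits poorly with wording that attributes the change to the strategies.

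Three further inferences are tempting and not supported:
- That the listed diagnostics are wrong for a survival model. Together with the transformations and time-point contrasts, they plausibly belong to an unnamed linear model of follow-up scores. The fair criticism is that this model is not named and that no proportional-hazards check is listed.
- That the curves would be drawn for the six scores listed as "Cigarette demand (Q0 and alpha), Craving (QSU Intention, QSU Relief), and Delay Discounting", so that region-by-score combinations can be counted. That list is given for the treatment phase, and the Analytical Plan says the phases are analysed separately. The follow-up paragraph names no score.
- That four curves confound the two serially run Aims. Plotting four groups is not pooling them for a test, and the same paragraph speaks of contrasts between two groups.

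The Exploratory Aim comes nearest to a rescue, since its hierarchical model also includes caudate signal change between smoking and neutral blocks. It still specifies no arm-by-baseline-reactivity term.

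**Conclusion.** The point holds in this form: the follow-up analysis, followed as written, does not test its stated hypothesis. This is more than missing detail, because even a completed log-rank comparison on reactivity would test prognosis. The simulation shows the size of the risk under assumed inputs: 52% to 74% positive findings with no moderation, and 4% to 5% detection of moderation that averages out. The percentages depend on the assumed hazards and slopes. The direction follows from the models and does not.

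The consequence is limited. Follow-up is a secondary goal, the sample size was set for the treatment phase, and no primary conclusion rests on this analysis. The correct test will itself be weak at this size, so it can support only exploratory statements. The plan should be changed, but the trial's main aims do not depend on it.

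**What to change.** Amend the SAP wording before follow-up data are examined. The protocol schedules data analyses at every 20% of recruitment, so this matters early.
1. Reconcile the quit-date statements in Table 1 and under Interventions and Interactions.
2. Define one smoking event that the collected data support, for example first lapse or relapse from TLFB, and from EMA only if EMA records smoking. State its time origin and censoring rule.
3. Within each Aim, fit a Cox model with arm, continuous baseline reactivity for one prespecified region and condition, their product, and the stratifiers. Take the product as the test of the hypothesis, and check proportional hazards.
4. For follow-up scores, name the linear longitudinal model to which the listed diagnostics and contrasts apply, and include the same interaction.
5. State how missing baseline MRI and the remaining regions and conditions are handled.
6. Label the analysis exploratory and report the interaction with its confidence interval.

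The cost is drafting time. No new data are needed. The price is an openly low-powered interaction test in place of tests that look more powerful but answer another question.
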